The following clinical data will be collected prospectively and structured in an electronic database: gender, age, primary tumor site, NET type (G1 or G2 or NET G3), Eastern Cooperative Oncology Group (ECOG) status, metastasis sites, degree of hepatic impairment (greater than or equal to less than 50 percent in conventional imaging), previous treatments, comorbidities (defined as any clinical condition requiring pharmacological therapy), concomitant medications of chronic use, body mass index, IHC expression intensity of HR, NET-related symptoms, time from the diagnosis of advanced disease to day 1 cycle 1 of tamoxifen, efficacy, adherence and toxicity results.

TABLE 1. Complete procedural summary of the study after signing the ICF

Procedure	Screening *	baseline evaluation	w S 3	S 6	w 12	w 18	w 24	w 30	w 36	w 42	w 48	Short visit [#]
			**	**	**	**	**	**	**	**	**	
Eligibility assessment												
Fulfills eligibility criteria	x											
Demographics data, medical history, and prior treatment		x										
IHC Request for Hormone Receptors (ER and / or RP) > 1 percent	x											
Provision of tamoxifen		x	x	x	x	x	x	x	x	x	x	x
Clinical safety assessment												
physical examination		x	x	x	x	x	x	x	x	x	x	x
Vital signs, body weight and ECOG		x	x	x	x	x	x	x	x	x	x	x

Assessment of signs and symptoms		x	x	x	x	x	x	x	x	x	x	x	x
Review of concomitant medications		x	x	x	x	x	x	x	x	x	x	x	x
Evaluation of adverse events			x	x	x	x	x	x	x	x	x	x	x
Laboratory safety assessment													
Blod count	x			x	x	x	x	x	x	x	x	x	x
Creatinine / urea	x			x	x	x	x	x	x	x	x	x	x
AST / ALT / bilirubin levels	x			x	x	x	x	x	x	x	x	x	x
Serum sodium / potassium	x			x	x	x	x	x	x	x	x	x	x
Pregnancy test in women of childbearing age	x												
INR, albumin	x												
Adherence assessment													
Adherence for days taken / month				x	x	x	x	x	x	x	x	x	x
Image evaluation													
CT scan of the chest, abdomen and pelvis ***	x				x		x		x		x		x
Tumor marker													
Specific hormone		x			x		x		x		x		x
Dosage of serum chromogranin A		x			x		x		x		x		x
Exploratory analysis													
PET-CT-Gallium 68 Somatostatin Receptors		x			x								
Collection of circulating tumor cells		x											

* within 21 calendar days of the first dose;

** window of - / + 3 days

***baseline examinations within 8 weeks of day 1; Resonance of abdomen and pelvis in special cases (allergy to iodinated contrast)

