Tamoxifen Citrate was the first selective modulator of the developed estrogen receptor. It is a prodrug that has, in itself, little affinity for its target protein, the estrogen receptor. Tamoxifen is metabolised in the liver by the CYP2D6 and CYP3A4 isoforms of cytochrome P450 in its active metabolites afimoxifene and endoxifen, which present 30-100 times more affinity for the estrogen receptor. These active metabolites compete with estrogen for the body binding to the estrogen receptor, possessing 178 percent and 338 percent more affinity for estrogen and alpha receptors, respectively, than estradiol. They have different activities depending on the target tissue. In mammary tissue, they act as receptor antagonists. In other tissues, such as the endometrium, it is agonist. Because of this variable activity, tamoxifen is considered a selective modulator of the estrogen receptor. In hormone receptor-positive breast cancer tumor cells, active metabolites bind to the receptor producing a nuclear complex that decreases DNA synthesis by modulating gene expression, inhibiting estrogenic proliferative effects. The antitumor effect occurs by maintaining the cells in the G0 and G1 phases of the cell cycle, therefore, being a cytostatic rather than cytotoxic agent. Since the demonstration of antineoplastic activity in breast cancer in clinical studies in 1971, tamoxifen has become the prototype drug for

hormone treatment of breast cancer patients positive for hormone receptors at all stages of the disease, both pre- and post- menopause.²¹

The metabolism of tamoxifen is complex (about 10 major metabolites have been identified) and is mediated in the liver by cytochrome P450. Metabolites are excreted mainly by bile. The initial plasma half-life of tamoxifen ranges from 4 to 14 hours, with a secondary half-life of approximately 7 days. The concentration stability of tamoxifen is reached after 4 to 16 weeks of treatment. This prolonged half-life reflects levels of plasma protein binding and enterohepatic recirculation. There is no need for adjustment for renal function and has not been studied in patients with severe hepatic dysfunction.

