- Within 21 days of the first dose of treatment: investigation of the immunohistochemical expression of RH in the paraffin-shaped tumor material. If expression \geq 1 percent, eligibility is confirmed and the following procedures are:

- Within 3 days of day 1 cycle 1: Medical history, including diagnosis and previous treatments, history of other diseases (active and resolved), medications in use and general demographic data. Complete physical examination, ECOG (PS) performance index, body weight and height, and vital signs.
- Laboratory tests: blood count, urea, creatinine, ALT, AST, total bilirubin, sodium, potassium, INR and albumin and pregnancy test for women of childbearing age will be performed within 3 days of the first dose of treatment; these patients will be directed to contraception.
- It will be accepted that baseline imaging has been performed within 8 weeks of the first dose of treatment: Computed tomography (or nuclear magnetic resonance, if applicable) of the abdomen, pelvis and chest.
- All of these above exams are already part of the routine in treating NET at the AC Camargo Cancer Center.

Security Assessment at Week 3:

Adherence and presence of adverse events will be assessed at this time (see Safety Assessment). Will be allowed window of +/- 5 days

Safety evaluation on other weeks:

At each medical appointment, the adverse effects and toxicity related to the treatment will be evaluated by means of anamnesis, physical examination and laboratory evaluation, as follows:

- Complete physical examination, measurement of vital signs, measurement of weight and height, ECOG, use of concomitant medications.
- Evaluation of adherence to treatment.
- Evaluation of adverse events

- Laboratory evaluation: blood count, urea, creatinine, ALT, AST, total bilirubin, sodium, potassium, and others, if clinically indicated.

To grade toxicities, we will use CTCAE 5.0 criteria. Patients who present intolerable grade 2 toxicity or grade 3 that the investigator judges to be related to tamoxifen will have the reduced dose of treatment (see TABLE 3) and will be conducted as previously discussed. All adverse effects will be graded and evaluated whether or not they are related to treatment.

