For evaluation of efficacy, patients will perform imaging (chest tomography, abdomen and pelvis or abdominal and pelvic resonance) at baseline and every 12 weeks until progression or intolerance. Patients will also be evaluated for signs and symptoms that may be related to disease progression. Patients who present clinical progression at the investigator's judgment, but without radiological progression, may discontinue treatment with tamoxifen and continue imaging until progression; however, if new treatment is instituted, the last date of receipt of tamoxifen will be the date of censure in the analysis of progression-free survival.

Patients will also be evaluated for somatostatin receptor expressiveness through the functional examination of PET-CT Gallium-68, which will be performed before treatment and at week 12, in addition to biochemical response through the dosage of chromogranin A and / or specific hormone every 12 weeks, in conjunction with imaging (tomography and / or resonance). An interval of +/- 5 days will be

allowed for imaging and PET-CT Gallium-68 exams. Patients with suspected progression (eg worsening of symptoms) may perform images within less than 12 weeks to assess progression of disease, at the discretion of the investigator.

After documentation of progression or exit from the study for other reasons, patients will be followed up by the investigator or other oncologist from the Clinical Oncology team for symptom control, imaging monitoring and possible future therapies. The patient continues to be cared for at the AC Camargo Cancer Center, if desired.

Other concomitant medications

In general, concomitant medications and therapies deemed necessary for the intensive treatment and safety of the patient are permitted provided that their use is documented in the patient's records and in the appropriate clinical record. Tamoxifen may have drug interaction with coumarin anticoagulants (Marcoumar, Marevan, Coumadin) and those with some of the new anticoagulants (Pradaxa, Xarelto). These drugs should be avoided during the study (moderate contraindication). Concomitant administration of investigational medicinal products is not permitted. Administration of any other anticancer agents including chemotherapy, target therapy and biological agents is not permitted.

Statistical Considerations

Statistical plan

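### The drug-interaction rule names only anticoagulants, so strong inhibitors of the enzymes that activate tamoxifen are allowed; a modest dilution of the 24-week disease control rate is possible

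*Combined protocol and SAP*

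**What the plan says.** All references are to the combined protocol and SAP.

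- **Treatment, Tamoxifen.** On the parent drug: "It is a prodrug that has, in itself, little affinity for its target protein, the estrogen receptor". On activation: "Tamoxifen is metabolised in the liver by the CYP2D6 and CYP3A4 isoforms of cytochrome P450 in its active metabolites". The metabolites are credited with 30 to 100 times more receptor affinity. The same section adds two cautions: "They have different activities depending on the target tissue", and "about 10 major metabolites have been identified". It puts stable concentration at 4 to 16 weeks.
- **Other concomitant medications.** The general rule is that "concomitant medications and therapies deemed necessary for the intensive treatment and safety of the patient are permitted provided that their use is documented". Coumarins and some newer anticoagulants are to be avoided because of interaction. Investigational products and other anticancer agents are not permitted. Enzyme inhibitors are not mentioned.
- **Exclusion criteria.** Oral anticoagulation, current tamoxifen and oncologic therapy within 3 weeks are listed. No enzyme inhibitor is.
- **Baseline Assessment and Table 1.** The scheduled history covers "history of other diseases (active and resolved), medications in use and general demographic data" and falls under the item that begins "Within 3 days of day 1 cycle 1: Medical history". Eligibility is checked at screening, "within 21 calendar days of the first dose". Co-medication is reviewed at baseline and at every later visit, and drugs in chronic use go into the database.
- **Statistical plan.** Everyone who takes at least one dose is evaluated for efficacy. No analysis or listing by co-medication is planned.

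**The concern.** The protocol identifies the two enzymes on which activation of its only study drug depends, and it has a paragraph on interacting drugs that includes an avoid category. That paragraph does not cover drugs that block those enzymes. An investigator following it has no prompt to replace such a drug, even where an equally good alternative exists.

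At stake is the primary outcome, the 24-week disease control rate. A patient whose tamoxifen is poorly activated would receive less active drug than intended and still count fully in the rate. If the active metabolites carry the benefit, the estimate is pulled towards the null. The error would be a missed signal; it would not create a false claim of activity. After a negative result, no planned output would show how many patients had been exposed.

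**Working it through.** **1. Is the gap covered elsewhere?** Setting the sections side by side: the Tamoxifen section names CYP2D6 and CYP3A4; the concomitant-medication section restricts three other drug classes; the exclusion list names no inhibitor; Table 1 and the Study design section record co-medication but give no instruction to act on it. The gap is real. Such drugs are permitted by omission, subject to being judged necessary and documented.

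**2. Inputs.**

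- From Sample Size Calculation: null rate 50%, target rate 70% (so an assumed effect of 20 points), N = 22.
- Not in the documents, so assumed: k, the number of the 22 patients on a strong inhibitor (0 to 4); L, the share of the 20-point effect that such a patient loses (0.5 or 1).

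The plan gives no figure for this dilution, so there is none to reproduce. N = 22 is taken as stated. The normal approximation with the plan's inputs gives [(1.645 × 0.5 + 0.842 × √0.21)/0.20]² = 36.5, so 37 evaluable before allowing for loss. That mismatch is a separate matter and is not relied on here.

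**3. Expected rate.** Rate = 0.70 − 0.20 × L × k/22. Each exposed patient costs 0.20 × 0.5/22 = 0.45 points at L = 0.5, and 0.20/22 = 0.91 points at L = 1.

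| k of 22 | L = 0.5 | L = 1 |
|---|---|---|
| 0 | 70.0% | 70.0% |
| 1 | 69.5% | 69.1% |
| 2 | 69.1% | 68.2% |
| 4 | 68.2% | 66.4% |

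**4. Against sampling error.** SE = √(0.7 × 0.3/22) = 0.0977, or 9.8 points. The largest drop in the table is 0.20 × 4/22 = 3.64 points, and 3.64/9.77 = 0.37 SE. A drop of one SE at complete loss needs 0.0977/(0.20/22) = 10.7, so 11 of 22 patients exposed (10 give 9.09 points, 0.93 SE; 11 give 10.0 points, 1.02 SE).

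**5. In power terms.** The plan states no decision rule. Assume success at 16 or more of 22, whose exact upper-tail probability at 50% is 0.026. Power at 70% is then 0.49. At complete loss it becomes 0.46 with one patient exposed, 0.42 with two and 0.35 with four. These figures depend on the assumed rule as well as on k and L.

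**The case against.** The strongest reply is that no harm is shown. The documents name no inhibitor, give no frequency of use, and do not say that blocking one of two activating enzymes reduces activity in neuroendocrine tumours. The protocol itself describes activity that varies by tissue and many metabolites, and it admits tumours positive for the progesterone receptor alone. Even complete loss of effect in 4 of 22 patients moves the rate by well under half a standard error. Counting every treated patient is the stated intention-to-treat approach and is not a fault. All of this stands. It limits the point to a possible, small loss in an assumed direction.

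A second reply is that permission already depends on the drug being judged necessary, so a soft avoid clause leaves clinical judgement where it was. That is partly right. The clause does, however, tell the clinician which drugs matter and prompts a search for an alternative, which the present text does not.

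A reader might also infer from the baseline item scheduled close to day 1 that co-medication is discovered too late to change. The documents do not support that. The screening eligibility check already requires asking about anticoagulants, tamoxifen and recent oncologic therapy. Co-medication is reviewed again at every visit. Stable concentration takes 4 to 16 weeks against a 24-week endpoint, so a switch at or soon after day 1 remains feasible.

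**Conclusion.** The point holds in a limited form: the interaction rule omits strong inhibitors of the enzymes that the protocol says activate the study drug, and this could modestly dilute the primary rate towards the null. The estimated 0 to 3.6 points assumes 0 to 4 of 22 patients exposed, loss of up to the whole 20-point effect in each, and an antitumour effect carried by the active metabolites. None of these can be checked from the documents.

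It would go too far to infer that the primary result is compromised or that dilution has been demonstrated. Type I error is not inflated. The change is worth considering because it is cheap, and for no stronger reason.

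**What to change.** In Other concomitant medications, after the anticoagulant sentences, add: *Strong CYP2D6 or CYP3A4 inhibitors should be avoided during the study where a suitable alternative exists; a patient already taking one is switched before or as soon as possible after day 1 if clinically appropriate, and may still enter if not.*

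Look for such drugs at the existing screening eligibility check and at each visit's co-medication review. The research pharmacy, which already dispenses tamoxifen, can keep the short list of drugs that count as strong inhibitors. The eligibility criteria stay as they are.

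Optionally, report a descriptive count of patients exposed at any time before week 24, from data already collected and without a test. With so few patients it could neither show nor rule out dilution; it would only make exposure visible.

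The cost is one sentence, a short drug list, and an occasional change of co-medication, made only if the treating clinician judges it safe. No patient is excluded. Some dilution may remain from patients who cannot be switched.

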Primary: Disease control rate at 24 weeks after initiation of tamoxifen (since day 1 cycle 1), defined by absence of radiological progression in conventional imaging

examinations by RECIST 1.1 (Appendix I). Isolated increase of biomarker (chromogranin A) or specific hormone will not be considered progression.

Secondary:

(1) Progression-free survival, defined by time from tamoxifen day 1 cycle 1 to death from any cause or radiological progression by RECIST 1.1, whichever occurs first. Patients alive and without progression at the time of study analysis will be censored for time-to-event analysis.

(2) Biochemical response will be defined by at least 30 percent drop in the marker (chromogranin and / or specific hormone) at any time of treatment in relation to pre-treatment value (s).

(3) Radiological response rate by RECIST criteria 1.1 during the study period.

(4) Disease control rate, defined by absence of radiological progression by RECIST 1.1 criteria, according to the intensity of expression by immunohistochemistry (IHC) of HR and also according to primary site (pancreas, gastrointestinal or lung) during the study period.

(5) Toxicities frequency: Adverse events of grades 2 or more by Common Adverse Event Toxicity Criteria (CTCAE) version 5.0 during the study period.

Exploratory:

(1) Evaluate possible variations in intensity and number of sites between PET-CT gallium-68 pre-treatment and 12 weeks after initiation of tamoxifen as a continuous variable for each capture lesion. Although this examination is part of the evaluation routine of NET, in this study we will evaluate differences in the intensity of uptake with tamoxifen.

(2) Evaluate the percentage of CTC positivity in NET, as well as average number of cells in case of positivity. To evaluate the presence of estrogen and progesterone receptors in CTC.

Methodology:

Study design:

A single-arm, unicentric, single-stage clinical study of tamoxifen for patients with well differentiated neuroendocrine tumors and radiological progression with positive (> 1 percent) HR (estrogen and / or progesterone) expression by IHC.

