#After 1 year of treatment the frequency of exams and visits will be every 12 weeks (+/- 3 days)

Methodology for research on the expression of Hormone Receptors (HR)

For the immunohistochemical study, the original blades of each case, stained by the hematoxylin-eosin method, will be re-evaluated by the study pathologist to select

the most representative and most preserved paraffin block of the tumor. From the chosen paraffin block, slides containing sequential sections (5-micrometer thickness) of the sample will be obtained and subjected to immunohistochemistry for estrogen receptor (ER) and progesterone receptor (PR). The entire immunohistochemical reaction will be performed in an automated platform using the Ventana Autostainer machine, following the BenchMark ULTRA® system (Ventana Medical Systems, Tucson, AZ, USA) and the Ultraview Universal DAB Detection Kit).

The protocol will follow the following steps:

1. The slides will be deparaffinized in EZ PREP solution (Ventana Medical Systems, Tucson, AZ, USA);
2. Antigen reactivation will be performed by heating in solution CC1 (Ventana Medical Systems Ultra Cell Conditioning Solution) at pH 9.0 to 96°C for 64 minutes;
3. Blocking endogenous peroxidase for 5 minutes using peroxidase blocking reagent (Ultraview Universal DAB Inhibitor, 3 percent H₂O₂);
4. Passages in Wash Buffer;
5. Incubation with the primary antibodies to ER and PR for 30 minutes;
6. Passages in Wash Buffer;
7. Incubation with HRP polymer (HRP Multimer) with subsequent washes in buffer;
8. Incubation with chromogen Diaminobenzidine (DAB), passage in wash buffer and counter-staining with Hematoxylin II;
9. Wash in water with detergent and then in distilled water;
10. Passage in xilol, alcohol and assembly of the blades.

Primary antibodies, dilutions, manufacturers, antigen retrieval methods and cutoff values used in the immunohistochemical study for evaluation of HR expression are presented in TABLE 2.

For the evaluation of the expression of estrogen and progesterone receptors, we will use previously published criteria in the literature. In this way, the cases in which more than 1 percent of the neoplastic cells show nuclear marking for these markers will be considered positive. In the absence of nuclear labeling or if it is present in less than 1 percent of the neoplastic cells, the research will be considered negative.^{16,17,18}

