Descriptive statistics will be used to report the results of categorical and continuous variables. The time-to-event variables will be reported in medians and Kaplan Meyer curves. The degrees of toxicity will be tabulated. The number of patients discontinuing treatment due to toxicity will be presented.

Efficacy and toxicity analyzes will be performed by intention to treat. Patients receiving at least one dose of tamoxifen will be evaluated for toxicity and efficacy.

Inferential analyzes of the primary outcome according to primary site and IHC HR expression intensity will be conducted to depend on the number of cases per subgroup; if possible, these analyzes will be performed with the chi-square test. The analyzes of intensity of uptake intensity to PET-CT gallium-68 will be with paired T-test. The CTC analysis will be presented in a descriptive way.

Sample Size Calculation

To calculate the sample size, we considered the disease control rate H0 at 6 months of 50 percent (placebo arm result of the phase III studies) 5,23 and H1 as a 6 months disease control rate of 70 percent. A 10 percent bitailed type I error was considered, 80 percent power loss and 30 percent follow up loss. With these calculations, the sample number will be 22 patients.

Recruitment and Study Duration

At the AC Camargo Cancer Center, 30 patients with advanced NET are treated annually. Therefore, considering the patients already under treatment and the possible candidates without previous treatment and that out of every 10 patients, N = 4 will meet eligibility criteria (NETs with positive HR), we estimate to recruit the study population in a maximum period of 3 years and have the first full evaluation in 3 ½ years.

Ethical Considerations

The study will be conducted in accordance with the protocol, Good Clinical Practice guidelines of the International Conference on Harmonization (ICH GCP) and applicable local laws and regulatory requirements. The Free and Informed Consent Term (ICF) must be in accordance with ICH GCP guidelines, local regulatory regulations, and legal requirements. See Appendix 2 for ICF.

The investigator should ensure that each study patient, or his / her legal representative, is fully informed about the nature and objectives of the study and

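### Disease control by HR expression is to be tested only by chi-square, with no HR scale or categories defined; a pre-specified rank test would use the order, need no cut point and be feasible at n = 22

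*Combined protocol and SAP*

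**What the plan says.** Secondary outcome (4), under Outcomes, is the disease control rate "according to the intensity of expression by immunohistochemistry (IHC) of HR and also according to primary site (pancreas, gastrointestinal or lung").

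Under Statistical Considerations, Statistical plan, the inferential analyses by site and by HR intensity "will be conducted to depend on the number of cases per subgroup", and "if possible, these analyzes will be performed with the chi-square test". No minimum count and no other test is named. The same section commits, without condition, to descriptive statistics for categorical and continuous variables.

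The only HR threshold is the one for positivity. The methodology section on HR expression counts as positive "the cases in which more than 1 percent of the neoplastic cells show nuclear marking", and Table 2 and the inclusion criteria use the same 1 percent level. This is an entry criterion, so it cannot separate enrolled patients from one another. ER and PR are stained separately, and either suffices for entry. The list of clinical data to be collected includes HR expression intensity but gives no scale for it.

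On size, Sample Size Calculation states: "With these calculations, the sample number will be 22 patients".

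**The concern.** Staining intensity, or percentage of stained nuclei, runs from low to high. A chi-square test can use it only after it has been cut into groups. With three or more groups the test ignores their order; with two, the information is lost in the cut itself. The plan fixes neither the groups nor the number of cases that makes the test possible, so both would be decided with the outcomes in hand.

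This bears on the rationale. The background suggests that the earlier tamoxifen study showed limited benefit partly because its patients were not selected for HR expression. Every patient here is HR-positive and there is no control arm, so the gradient among positives is the information the trial itself yields on that premise. It should be analysed by a rule fixed in advance that uses the whole reading.

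**Working it through.** **Inputs.** From Sample Size Calculation: N = 22, control 50% under H0 and 70% under H1, and 30% loss. From Outcomes: three primary sites. Assumed, because the documents give none: a two-sided 5% level for this secondary analysis, all gradients of control over HR, and the expected-count convention.

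**The plan's own figure.** The inputs are "we considered the disease control rate H0 at 6 months of 50 percent", "H1 as a 6 months disease control rate of 70 percent" and "A 10 percent bitailed type I error was considered, 80 percent power loss and 30 percent follow up loss", with the power read as 80%. The one-sample formula gives ((1.645 × √(0.5 × 0.5) + 0.842 × √(0.7 × 0.3)) / 0.2)² = ((0.822 + 0.386) / 0.2)² ≈ 36.5, so 37 evaluable, and 37 / 0.7 ≈ 53 after loss. The stated 22 does not reproduce. That is a separate matter; 22 is used below because it is the planned number.

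**Step 1: expected counts.** For a group of size g with X controlled patients out of N, the smaller expected count is g × min(X, N − X) / N.

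- Three groups: the smallest group has at most 7 patients and the smaller outcome class at most 11, so the best case is 7 × 11 / 22 = 3.5. The convention needs 3 × 5 × 2 = 30 patients. Enumerating every three- and four-group split of 22 finds none that meets it, nor the looser Cochran rule (no expected count below 1, at most 20% below 5). Primary site falls here.
- Two groups: an 11/11 split needs 11 × min(X, 22 − X) / 22 ≥ 5, so X from 10 to 12. A 10/12 split needs X = 11. More uneven splits never qualify.

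| True control rate | 11/11 split, P(10 ≤ X ≤ 12) | 10/12 split, P(X = 11) |
|---|---|---|
| 50% | 47.7% | 16.8% |
| 60% | 32.1% | 10.7% |
| 70% | 8.7% | 2.5% |
| 80% | 0.6% | 0.1% |

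- If 30% loss leaves 15 or 16 evaluable (22 × 0.7 = 15.4), the best two-group case is 8 × 8 / 16 = 4, so the convention is never met.

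**Step 2: does missing the convention spoil the error rate?** Hardly. With groups of 8/7/7 and 60% control throughout, the exact size of Pearson chi-square is 4.5% at nominal 5% and 11.7% at nominal 10%.

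**Step 3: what ignoring order costs.** Simulation with a continuous HR score, N = 22, average control about 60%, 4,000 runs per row, 5% level. The gradient is the logit slope per standard deviation (SD) of the score. With the mid-point logit taken as ln(0.6 / 0.4) = 0.41, a slope of 1.0 means control of about 36% at one SD below the mean and 80% at one SD above.

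| Slope | Rank-sum | Chi-square, median split | Chi-square, tertiles | Gain (points) |
|---|---|---|---|---|
| 0 | 4.7% | 5.1% | 4.5% | – |
| 0.7 | 26.8% | 21.5% | 18.1% | 5.3 and 8.7 |
| 1.0 | 44.1% | 34.2% | 29.4% | 9.9 and 14.7 |
| 1.5 | 73.4% | 58.8% | 54.6% | 14.6 and 18.8 |

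If HR is instead a three-level ordinal score (8/7/7), exact enumeration compares Pearson chi-square with a Cochran-Armitage trend test:

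| Control by level | Chi-square | Trend | Exact chi-square | Exact trend |
|---|---|---|---|---|
| 40/60/80% | 25.6% | 32.3% | 22.7% | 29.5% |
| 50/70/90% | 26.4% | 38.2% | 23.9% | 32.3% |
| 30/60/90% | 58.2% | 68.6% | 54.8% | 65.4% |

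**Step 4: primary site.** Site is nominal, so only Step 1 applies to it. The exact (Fisher-Freeman-Halton) version is somewhat weaker than Pearson: 22.7% against 25.6%, and 54.8% against 58.2%, in the first and third rows above.

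**The case against.** A reader might infer that secondary outcome 4 will be dropped. The documents do not support that: only the inferential test is conditional, and rates by subgroup would still be described.

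A reader might also infer that chi-square cannot be run under the plan's own condition. The plan's condition is the number of cases per subgroup, with no threshold; the expected-count rule is a convention brought in from outside. Step 2 shows that the test would hold roughly its nominal error anyway, so its p-value would not be invalid. The conditional wording can even be read as leaving another test open. All of this stands, and it moves the case from validity to power and pre-specification.

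The documents speak of intensity and never say that the analysed reading is the percentage of stained nuclei; that percentage defines positivity only. It would be wrong to treat the scale as known. This too stands, but it adds to the gap: neither the scale nor the combination of ER and PR is defined.

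Finally, the gain is modest at shallow gradients, the gradients are assumed, and power is low with any test. The background also reports that HR-positive tumours may have a more favourable course, so a gradient in a single-arm trial cannot separate a tamoxifen effect from prognosis. A better test does not change that. It does make fuller use of data already collected, at almost no cost.

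**Conclusion.** The point holds as an inexpensive improvement to a secondary analysis. For HR expression, chi-square is a weaker choice than a rank or trend test. The loss is about 5 to 19 points of power at 22 patients, with similar error near 5%, if control rises or falls steadily with expression at the assumed slopes.

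The test meets the usual count convention never with three groups, and in 9% (70% control) to 48% (50% control) of trials with an even two-group split. An analyst who applies that convention would usually skip the test, and one who does not must still choose the groups. With neither groups nor threshold stated, both decisions could follow the data.

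The count result is specific to 22 patients, and a larger sample would relax it; the points on order and undefined categories would remain. The order argument applies to HR only. For primary site the gain is feasibility, not power.

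**What to change.** In the Statistical plan, replace the sentence on the chi-square test with wording such as:

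> HR expression is analysed on [scale to be named: for example percent of stained nuclei, or an ordinal intensity score], for ER and PR separately. The uncategorised reading is compared between patients with disease control and patients with progression by an exact Wilcoxon rank-sum test allowing for ties (an exact trend test if the scale is ordinal). The disease control rate in each HR and primary-site subgroup is reported with an exact confidence interval, whatever the subgroup size.

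Remove the conditional phrase. If subgroup rates by HR are wanted for display, fix those groups now as well. Analysing ER and PR separately is one option; any other rule serves if it is stated before the outcomes are known.

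An exact test across the three sites may be added. It can always be run, but has slightly less power than chi-square.

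The cost is plan wording only, with no extra patients, visits or assays. The report should say that power is low unless the gradient is steep, and that a gradient may reflect prognosis as well as treatment.
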